4.3. Data Collection, Management and Analysis

4.3.1. Data Collection

Data Collection Methods

Trial outcomes comprise routinely collected data which are housed at ICES. Access to all outcome data has been agreed upon with ICES.

Retention

Emergency Departments

Once randomization of the study sites is completed, the Principal Investigator will contact members of the Department of Psychiatry and Department of Emergency Medicine at each intervention site to be site co-Investigators, to assume responsibility for all study-related activities at their respective site. They will act as study "champions" and, in conjunction with Research Assistants, will provide study support to Emergency Department staff members.

Each study site will also receive training, as described in Section 4.1.3 Interventions, in the identification and management of self-harm as well as access to an electronic booking system for study referrals and Research Assistant(s) to coordinate all study-related activities.

Participants

This study will focus on the evaluation of a complex intervention based on routinely collected population-level health data. Given this, there will be no individual participant

recruitment for this study. All data collected through ICES will thus be included in the primary analysis irrespective of uptake of the smartphone-assisted PST.

4.3.2. Data Management

All electronic and hardcopies the study Case Report Forms will be stored at the Coordinating Study Site in areas with limited access. All electronic data will be stored on a secured server at The Ottawa Hospital. Once all data monitoring, validation and cleaning activities are complete, these records will be archived at a secure storage facility for a period of ten years, as required by ICH GCP guidelines.

4.3.3. Statistical Methods

Outcomes

The unit of analysis will be the individual patient. To evaluate the effectiveness of the complex intervention at population-level (primary trial analysis), all outcomes will be obtained from ICES, regardless of whether men received or participated in the study therapy. Dichotomous primary and secondary outcomes will be described, by arm, using frequencies and percentages. The primary composite outcome as well as its individual components (completed suicides and re-presentations within 1 year) will be compared between the intervention and control sites using generalized linear mixed effects regression, accounting for the pre-and post-intervention measures using repeated cross-sectional analysis [51]. Differences between the arms will be expressed as absolute and relative differences in proportions, together with 95% confidence intervals. Models will account for clustering at the Emergency Department level and over time using random effects. Cluster level covariates for factors used in the allocation procedure, namely urban/rural, onsite psychiatric service, and size will be included in regression models. Additional analyses will adjust for individual prognostic variables including age, ethnicity, pre-specified comorbidities (such as previous hospitalizations for substance use), and repeat as compared with first-time presentations for self-harm.

All binary secondary outcomes (representation to the ED for any reason, admission to hospital for any reason, and mortality for any reason) will be analyzed as described for the primary outcome. Length of hospital stay for any reason, number of hospital outpatient appointments, number of primary care appointments and cost data will be analyzed as described for the primary outcome, that is, using generalized linear mixed effects regression, but with either the Poisson or negative binomial distribution and using the log link function. Differences between the arms will be expressed as rate ratios together with 95% confidence intervals.

Additional subgroup analyses will be carried out for the following subgroups: first time presentations of self-harm compared to repeat presentations; Francophone versus Anglophone; men with substance abuse disorders versus no substance abuse disorder; and rural versus urban residence.

Health Economic Evaluation

We will conduct a cost-utility analysis from health system's perspective to assess the value for money of the smartphone-assisted PST compared to standard clinical care. A decision analytic model will be used to synthesize data on resource use, clinical outcomes, and health utility values obtained from the trial and the published literature. Costs associated with the intervention will be summarized over the one-year period. Total costs of the intervention will include the cost of smartphone-assisted PST development, training, data plan, supplies/materials and costs associated with the health care use over the one-year period. We will use a micro-costing technique by identifying, measuring, and valuing resources used [52]. Health care resource use will be obtained from the health administrative databases housed at ICES which contain information on physician visits including primary care and specialists, inpatient hospital admissions, including mental health institutions, emergency and ambulatory care visits, home care and rehabilitation claims, use of laboratory services, and prescription drug claims for those with high drug costs compared to their income. The efficacy of the smartphone-assisted PST will be obtained from the concurrent trial while the health utility values associated with self-harm and smartphone-assisted PST will derived from the concurrent cohort study. A one-year time horizon will be adopted in a base case analysis, and a lifetime horizon will be used in a scenario analysis. As a secondary analysis, we will take the societal perspective and include productivity loss in a cost calculation. The loss of productivity data will be gathered from the published literature.

An incremental cost per one additional quality-adjusted life year (QALY) gained will be estimated. Uncertainty in the analysis will be assessed using one-way and probabilistic sensitivity analyses. The cost-utility analysis will adhere to the best practices for conducting and reporting of health economic evaluations[53-54]. Both costs and health outcomes will be discounted using an annual rate of 1.5% as recommended by the Canadian Agency for Drugs and Technologies in Health. The analysis will be performed by a health economist at the Ottawa Methods Centre and will be overseen by [name].

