4.1.5. Sample Size

Power calculations for this trial were carried out within the logistical and practical constraints of the trial; in particular, a maximum of 25 sites are available for randomization, whereas the intervention can be implemented at only 10 sites. Consistent with previous clinical trials, we would consider a minimum relative reduction of 50% in the repetition rate to be both clinically important and achievable [47-49]. To conduct an accurate power calculation, we obtained data from ICES regarding the number of presentations with selfharm by men and the re-presentation rate to every hospital in Ontario from 2012 to 2014. Using these data, we calculated an anticipated baseline repetition rate (primary outcome) after 12 months of 13%. We also calculated an intracluster correlation coefficient (ICC) of 0.01 and an inter-period correlation of 0.008 (to account for over time correlations between pre- and post-intervention measures of the primary outcome). Given an average cluster size of 80 men and a coefficient of variation of cluster sizes (to account for imbalances in sizes) of 30%, 10 intervention clusters and 15 control clusters (2000 men) achieve 90% power to detect the minimum important difference. With 80% power, the detectable difference is a relative reduction of 41%, i.e., from a control arm rate of 13% to an intervention arm rate of 7.7% (an absolute reduction of 5.3%).

> Study Protocol Version 1, Date: December 1, 2017 Page 20 of 51

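### Three baseline prognostic variables already held in ICES data are left out of the primary model, so a case-mix change that differs by arm between periods goes unadjusted in the main estimate

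*Protocol*

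**What the plan says.** Protocol section 4.3.3 (Statistical Methods, Outcomes) analyses the primary composite with a generalized linear mixed model. It uses pre- and post-intervention data as repeated cross-sections, with random effects for Emergency Department and time. "Cluster level covariates for factors used in the allocation procedure" enter the model: urban/rural, onsite psychiatric service and size. Individual-level adjustment comes afterwards: "Additional analyses will adjust for individual prognostic variables", with age, ethnicity, comorbidities such as previous substance-use hospitalization, and repeat versus first presentation given as examples. Effects are to be reported as absolute and relative differences in proportions.

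Table 2 (section 4.1.4) lists age, previous hospitalization for self-harm and previous hospitalization for substance use as baseline prognostic measures with ICES sources. Their stated purpose is to assess subgroup differences. Ethnicity has no row.

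Section 4.2.1 constrained allocation on urban/rural, onsite psychiatry, size and men's 12-month re-presentation rate (maximum difference 3%). The last of these is not among the site covariates in section 4.3.3; the pre-period outcome carries it.

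**The concern.** Men enter the dataset through coded presentations (section 4.1.2) after sites have been allocated. Section 4.3.1 provides training in identifying and managing self-harm. In context this reaches only intervention sites, since section 4.2.2 keeps control sites unaware of the study. Section 3.1.1 describes self-harm as chronically under-detected and inconsistently recorded. Training could therefore change who is identified and coded as an index case, in one arm and only after the intervention starts.

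Such a change would not be visible in the pre-period, and fixed site characteristics would not absorb it. If it altered the share of higher-risk men, such as repeat presenters, it would move the primary estimate. The variables that could correct the measured part of it are already in hand but are used only in a secondary analysis with an open-ended covariate list.

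**Working it through.** **Inputs from section 4.1.5.** Control rate: "anticipated baseline repetition rate (primary outcome) after 12 months of 13" percent. Detectable difference at 80% power: "from a control arm rate of 13% to an intervention arm rate of 7.7" percent, which is 5.3 points. The protocol gives "an average cluster size of 80 men", a coefficient of variation of cluster size of 0.30, and an "intracluster correlation coefficient (ICC) of 0.01 and an inter-period correlation of 0.008". There are 15 control and 10 intervention sites. Two-sided 5% is assumed, in line with the 95% intervals in section 4.3.3. The 80 men per site are taken as the post-period size.

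**Reproducing the plan's power.** Design effect = 1 + [(1 + 0.30²) × 80 − 1] × 0.01 = 1 + 86.2 × 0.01 = 1.862. With 1,200 and 800 men divided by 1.862, power for 13% versus 7.7% is 79.2% (pooled z), 81.9% (unpooled z) or 78.5% (t, 23 df). The stated 80% reproduces. On the same basis the "minimum relative reduction of 50% in the repetition rate" has 94.0% power, so the statement that "10 intervention clusters and 15 control clusters (2000 men) achieve 90% power" is conservative on this basis.

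Standard error of the risk difference = √[1.862 × (0.13 × 0.87/1,200 + 0.077 × 0.923/800)] = 0.0185, or about 1.85 points.

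**Precision from adjustment.** Let the covariates explain R²w of within-site and R²b of between-site variance. The design effect becomes 0.99 × (1 − R²w) + 0.872 × (1 − R²b), where 0.872 = 87.2 × 0.01. The protocol gives no R² values, so these are assumptions.

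| R²w | R²b | Design effect | Power, 13% vs 7.7% |
|---|---|---|---|
| 0 | 0 | 1.862 | 79.2% |
| 1% | 0 | 1.852 | 79.4% |
| 5% | 0 | 1.812 | 80.3% |
| 10% | 0 | 1.763 | 81.4% |
| 0–10% | 25–50% | 1.644–1.327 | 84–91% |

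With R²b = 0 the standard error falls by 0.3% to 2.7%. If the pre-period is used as a baseline covariate, the correlation of site means is 87.2 × 0.008/1.862 = 0.375 and the design effect is 1.862 × (1 − 0.375²) = 1.60. Power is then 85.0% unadjusted, and 85.3–87.6% for R²w of 1–10%.

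**Shift from a case-mix change.** Let a share q of men be repeat presenters with risk ratio k, and hold the overall risk at 13%. The risk in the others is p₀ = 0.13/[1 + q(k − 1)], and the gap is p₀(k − 1). A differential change of 5 points in the share shifts the risk difference by 0.05 × gap.

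- q = 0.5, k = 1.5: p₀ = 0.104, gap = 0.052, shift = 0.26 points.
- q = 0.3, k = 2: p₀ = 0.100, gap = 0.100, shift = 0.50 points.
- q = 0.2, k = 3: p₀ = 0.093, gap = 0.186, shift = 0.93 points.

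Over q = 0.2–0.5 and k = 1.5–3 the range is 0.26–0.93 points. That is 5–18% of 5.3 points and 0.14–0.50 of a standard error. A single predictor of this kind explains only 0.5–4.9% of outcome variance (q(1 − q) × gap²/(0.13 × 0.87)), which is why the precision gain is small.

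**The case against.** The strongest reply is that the plan already protects the primary comparison. Allocation was constrained on men's re-presentation rate, the main component of the composite. The model uses the pre-period outcome, and an individually adjusted analysis is planned. Much of this stands. A stable difference between sites is removed in full by a change-from-baseline contrast, and in part if the baseline is down-weighted. A reader might infer that any imbalance in repeat presenters passes straight into the primary estimate. The documents do not support that; it applies to a change between periods that differs by arm.

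A reader might also infer that the primary result would be the more biased of the two analyses. That is not shown. Sites were randomized, chance imbalance is reflected in the interval, and the protocol contains no evidence that training changes who is coded. Adjustment would correct only what the three measured variables carry.

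Nor should a large imbalance be treated as expected. A 10-point gap would shift the estimate by 0.5–1.9 points. But with a 35% share (assumed) and the outcome's design effect, the standard error of the arm difference in share is √[1.862 × 0.35 × 0.65 × (1/800 + 1/1,200)] = 3.0 points. Ten points is then about 3.4 standard errors. With a covariate ICC of 0.05 (design effect 5.31, standard error 5.0 points) it is still about 2.

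Sparse outcomes are a fair objection to extending the model. At the 2.7% one-year suicide rate in men cited in section 3.1.1, 2,000 men give about 54 suicides, too few to add covariates comfortably. This is met by confining the change to the composite, at about 13%.

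Finally, the illustration uses repeat presenters, whereas Table 2 lists previous hospitalization for self-harm. The size is indicative only.

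**Conclusion.** The point holds as a modest improvement to an analysis choice. The protocol contains no error or contradiction here. The primary model leaves unadjusted a change in measured case mix that differs by arm between periods, although the three variables that could address it are available at baseline. For an assumed 5-point differential change the shift is about 0.3–0.9 points, less than half to about half of a 1.85-point standard error. The shares, risk ratios and size of change are all assumptions, since the protocol gives none.

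The case rests on robustness rather than power. A reader might infer a material loss of power, but if only within-site variance is explained the gain is about 0.2–2.2 percentage points. Larger gains would require the covariates to explain 25–50% of between-site variance, for which the document offers no figure.

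**What to change.** For the primary composite outcome, name age, previous hospitalization for self-harm and previous hospitalization for substance use in the primary model, alongside the site factors and period terms. State that all three are measured before the index episode, so that the index visit cannot count as history. Obtain the absolute and relative differences by standardization, which keeps them as differences in proportions, as section 4.3.3 already intends. Report the model without these covariates as a sensitivity analysis.

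Leave ethnicity in the additional analyses, since Table 2 gives no source for it. Do not require the extra covariates for sparse outcomes such as suicide alone. As section 4.3.3 analyses the components and other binary outcomes in the same way as the composite, this exception needs to be written down.

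No new data collection is needed. The cost is a short change of text and a standardization step, with intervals that allow for the 25 sites.

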Health condition(s) or problem(s) studied	Self-harm
Intervention(s)	Intervention: smartphone-assisted Problem-Solving Therapy (PST)

World Health Organization Trial Registration Data Set Items

DATA CATEGORY	INFORMATION
	Control: standard clinical care
Key inclusion and exclusion criteria	Ages eligible for study: ≥18 years Sexes eligible for study: Male Accepts healthy volunteers: No Inclusion criteria: adult patient (≥ 18 years); patient identifies as male, patient presents to Emergency Department for an index episode of intentional self-harm at an eligible Emergency Departments in Ontario, Canada. Exclusion criteria: patient presents to an eligible Emergency Department for a reason other than intentional self-harm.
Study type	Interventional Allocation: randomized, unbalanced Intervention model: parallel assignment Masking: none Primary purpose: prevention
Date of first enrolment	Pending
Target sample size	25 hospitals; anticipated total sample size of approximately 2,000 men
Recruitment status	Active, not yet recruiting
Primary outcome(s)	Composite measure of suicides and/or proportion of re-presentations to any Emergency Department in Ontario for intentional self-harm
Key secondary outcomes	Within one year of enrollment:
	• Number of suicides;
	• Proportion of self-harm re-presentations to any

DATA CATEGORY	INFORMATION
	Emergency Department in Ontario;
	• Proportion of re-presentations for any reason to any Emergency Department in Ontario;
	• Proportion of hospital admissions for any reason to any hospital in Ontario;
	• Length of stay at any hospital in Ontario for any reason;
	• Proportion of hospital outpatient appointments for any reason at any hospital in Ontario;
	• Number of deaths (mortality rate), for reasons other than suicide and undetermined deaths;
	• Proportion of primary care visits, defined as any visit to a general practitioner;
	• Total health care costs for the treatment of self-harm;
	• Physician costs for the treatment of self-harm;
	• Emergency Department costs for the treatment of self-harm;
	• Hospitalization costs for the treatment of self-harm;
	• Other costs related to the treatment of self-harm.

Table of Contents

1.	FUNDI	NG	8
2.	ROLES	AND RESPONSIBILITIES	8
2	.1. Contr	ibutorship	8
	2.1.1.	Author's Contributions	9
	2.1.2.	Sponsor contact information	9
2	.2. Com	nittees	9
	2.2.1.	Principal Investigator and co-Principal Investigator:	9
	2.2.2.	Steering Committee (refer to title page for membership)	9

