Self-harm has a strong association with suicide: 1.6% of people presenting to Emergency Departments with self-harm will die by suicide within one year (95% confidence interval 1.2 to 2.1%), with the incidence rate being almost double in men compared to women (2.7% vs 1.2%) [8]. Approximately four percent of individuals who have presented to the Emergency Department for the treatment of self-harm die by suicide within five years of their index presentation [8]. This risk is more than 50 times greater than the general population rate and is associated with a 40-year reduction in average life expectancy [8]. A recent population-based cohort study investigating administrative datasets in the province of Ontario discovered that: "all-cause mortality following a first episode of self-poisoning was 1,107 per 100,000 person-years...[with] nearly half of all deaths being suicides, accidents or [of] undetermined intent"[9].

Presentation to the Emergency Department with self-harm is a major identifiable risk factor for suicide, with at least one quarter of deaths by suicide being preceded by a hospital visit due to non-fatal self-harm in the previous year [10-11]. As such, it is likely that any reduction in the repetition of self-harm will be mirrored by a decline in subsequent deaths by suicide. The Canadian Association for Suicide Prevention (CASP) blueprint for a national suicide prevention strategy has also identified people who have attended hospital because of non-fatal self-harm as a high risk group to target in order to prevent suicide [12]. Mortality from non-suicidal causes is also high for those who self-harm, with significantly more than the expected numbers of deaths from natural causes and from accidents [13]. These premature deaths are greatly over-represented among young people and the potential years of life lost in the community are many.

Individuals who self-harm are frequent users of health and social services [14]. Approximately 10% of those who present in an Emergency Department following self-harm will engage in repeat self-harm in the following month and up to 27% after six months [15]. Recurrent self-harm is associated with significant distress and many unresolved interpersonal problems [16].

Why Focus on Men?

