3.3.2. Secondary Hypotheses and Objectives

The key secondary objectives are to determine, compared to usual care, whether the provision of a service that delivers smartphone-assisted PST specifically designed for men who present to the Emergency Department with self-harm, results in:

- 1. Lower suicide rates;
- 2. Fewer contacts with any Emergency Departments in Ontario for the repetition of self-harm;
- 3. Fewer contacts with any Emergency Department in Ontario for any reason;
- 4. Fewer admissions to hospital for any reason;
- 5. Fewer outpatient appointments for any reason at any hospital in Ontario;
- 6. Lower mortality rates, not related to suicide;
- 7. Lower use of primary care services (defined by contact with a family physician); and/or
- 8. Decreased costs to the health care system, including physician, hospitalization, Emergency Department, and other costs.

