4.1.4. Outcomes

The primary outcome measure will be a composite of the incidence of suicides and/or re-presentations to any Emergency Department in Ontario for self-harm in the year after the index episode of self-harm. The incidence of suicide and re-representation to Emergency Department will be measured using ICD-10-CM codes T360-T50992, T510-T6592, T71112-T71232, X71-X83 (refer to Appendix A for full list of codes and descriptors) [46]. Individuals who died by suicide will be identified in ICES using the Vital Statistics - Death Database. A potential problem with the outcome measures in this trial is that the intervention may also change help-seeking behaviour. That is, men may seek out healthcare that they would not have in the past, which may lead to an increase in re-presentations to the Emergency Department for patients in the intervention group. In order to explore changes to health-related help-seeking, we will also collect data on primary care and hospital outpatient care not driven by emergencies through ICES. This will be measured in ICES, using the Ontario Health Insurance Plan (OHIP) Claims Database and National Ambulatory Care Reporting System Metadata (NACRS). We will also address this through a sub-study of smartphone-assisted PST.

The secondary outcome measures will include total number of suicides; representations to any Emergency Department in Ontario for the repetition of self-harm; representations to any Emergency Department in Ontario for any reason; other health system use including use of primary care and hospital outpatient appointments; mortality not related to suicide; and, health system costs within one year which will inform an economic analysis. All outcomes will be identified and measured using routinely collected data housed at ICES. Men who present with intentional self-harm in the study Emergency Departments will be identified from ICES administrative health data.

	Justification	Data Source	Data Collection Period
Primary Outcome Va	riable (composite outco	ome variable)	
Death by Suicide	To assess the clinical	ORGD, NACRS	Baseline; 12 months
and/or re-	impact of the	(ICES)	
presentation to any	provision of a		
Emergency	smartphone-assisted		
Department in	PST service.		
Ontario for Self-harm			
Secondary Outcomes	Secondary Outcomes		
Death by Suicide	To assess the clinical	ORGD (ICES)	Baseline; 12 months
	impact of the		
	provision of a		
	smartphone-assisted		
	PST service.		

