Re-presentation to	To assess the clinical	NACRS (ICES)	Baseline; 12 months
any Emergency	impact of the		
Department in	provision of a		
Ontario for Self-harm	smartphone-assisted		

Table 2. Outcome Measures

	PST service.		
Re-presentation to any Emergency Department for any reason	To assess the clinical impact of the provision of a smartphone-assisted PST service.	NACRS (ICES)	Baseline; 12 months
Admission to any hospital in Ontario for any reason	To assess the clinical impact of the provision of a smartphone-assisted PST service.	NACRS (ICES)	Baseline; 12 months
Hospital outpatient appointments in Ontario for any reason	To assess the clinical impact of the provision of a smartphone-assisted PST service.	OHIP (ICES)	Baseline; 12 months
Primary care appointments	To assess the clinical impact of the provision of a smartphone-assisted PST service.	OHIP (ICES)	Baseline; 12 months
Mortality for reasons other than suicide	To assess the clinical impact of the provision of a smartphone-assisted PST service.	ORGD (ICES)	Baseline; 12 months
Total Health Care Costs	To assess the economic impact of the provision of a smartphone-assisted PST service.	OHIP, DAD, NACRS, NRS, CCRS, OMHRS, ODB, ADP (ICES)	Baseline; 12 months
Physician Health Care Costs	To assess the economic impact of the provision of a smartphone-assisted PST service.	OHIP (ICES)	Baseline; 12 months
Emergency Department Health Care Costs	To assess the economic impact of the provision of a smartphone-assisted PST service.	NACRS (ICES)	Baseline; 12 months
Hospitalization Health Care Costs	To assess the economic impact of the provision of a smartphone-assisted PST service.	DAD (ICES)	Baseline; 12 months
Other Health Care Costs	To assess the economic impact of the provision of a	NRS, CCRS, OMHRS, ODB, ADP (ICES)	Baseline; 12 months

	smartphone-assisted		
	PST service.		
Prognostic outcome n	neasures		
Age	To assess differences	RPDB (ICES)	Baseline
	between subgroups.		
Previous	To assess differences	NACRS (ICES)	Baseline
hospitalization for	between subgroups.		
self-harm			
Previous	To assess differences	NACRS (ICES)*	Baseline
hospitalization for	between subgroups.		
substance use			

* Appendix B for list of ICD-10-CM codes.

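### Section 4.3.3 names all-cause mortality as the secondary mortality outcome to be modelled, where four other places in the protocol define mortality excluding suicide

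*Protocol*

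**What the plan says.** Section 4.3.3 introduces the analysis of the secondary outcomes with "All binary secondary outcomes (representation to the ED for any reason, admission to hospital for any reason, and mortality for any reason", and says these will be handled in the same way as the primary outcome. The same section has already provided for a comparison of the primary composite and "its individual components (completed suicides and re-presentations within 1 year", so suicide has its own analysis.

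The mortality outcome is defined in four other places:

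- Registration data set, key secondary outcomes: "Number of deaths (mortality rate), for reasons other than suicide and undetermined deaths".
- Section 3.3.2, objective 6: "Lower mortality rates, not related to suicide".
- Section 4.1.4, text on secondary outcomes: "mortality not related to suicide".
- Section 4.1.4, Table 2: "Mortality for reasons other than suicide", with the death database (ORGD) as its source.

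On a separate matter, Table 2 gives NACRS as the only source for hospital admissions and for the two baseline variables on previous hospitalization, and DAD as the source for hospitalization costs. The key to the table expands NACRS as an ambulatory care system and DAD as a discharge abstract database.

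**The concern.** The analysis section names a different endpoint from the one that the objectives and the outcome definitions set up. All-cause mortality includes suicide, and objective 6 concerns deaths that are not suicides.

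This affects interpretation. If the service lowered suicides and left other deaths unchanged, an all-cause analysis could show a mortality benefit that objective 6 does not ask about. If it lowered suicides while other deaths rose, the two could offset each other and the rise would be hidden. The same suicides would also count in three reported comparisons: the composite, its suicide component and the mortality outcome.

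The four definitions also differ on one point. The registration data set sets aside undetermined deaths as well as suicides, and the other three set aside suicides only. Correcting section 4.3.3 alone would leave two definitions of non-suicide mortality in force.

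**Working it through.** The protocol gives no expected number of deaths, so there is no figure of its own to reproduce. The check is a comparison of the texts, followed by an illustration of size.

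**Comparison of the texts**

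| Place | Suicides counted? | Undetermined deaths counted? |
|---|---|---|
| Registration data set | No | No |
| 3.3.2, objective 6 | No | Not excluded |
| 4.1.4, text | No | Not excluded |
| Table 2 | No | Not excluded |
| 4.3.3, outcome to be modelled | Yes | Yes |

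Section 4.3.3 stands alone in counting suicides. No section lists all-cause mortality as a further outcome, so the phrase cannot be read as naming an extra endpoint defined elsewhere.

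**How many suicides might be involved**

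Inputs:

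- Section 4.1.5: 10 intervention and 15 control clusters averaging 80 men, so 10 × 80 = 800 and 15 × 80 = 1,200, 2,000 in total.
- Section 3.1.1, one-year suicide rate by sex: "with the incidence rate being almost double in men compared to women (2.7% vs 1.2" (per cent).
- Section 3.1.1, both sexes: "1.6% of people presenting to Emergency Departments with self-harm will die by suicide within one year (95% confidence interval 1.2 to 2.1" (per cent).
- Section 3.1.1, Ontario cohort after a first self-poisoning: all-cause mortality of 1,107 per 100,000 person-years, with nearly half of the deaths being suicides, accidents or of undetermined intent.

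Expected count = number of men × one-year rate.

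- Rate in men: 0.027 × 2,000 = 54 suicides (0.027 × 800 = 21.6 intervention; 0.027 × 1,200 = 32.4 control, with no treatment effect).
- Rate in both sexes: 0.016 × 2,000 = 32. Confidence limits: 0.012 × 2,000 = 24 and 0.021 × 2,000 = 42.
- Ontario cohort, taking 2,000 person-years: 2,000 × 1,107 / 100,000 = 22.1 deaths from all causes. Half of that is 11.1. Since nearly half covers suicides, accidents and undetermined deaths together, suicides alone would be fewer than about 11.

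The sources do not agree. The suicide count from either pooled rate (54 or 32) exceeds the total number of deaths implied by the Ontario cohort (22). The populations differ: one pooled rate covers both sexes, the Ontario cohort is limited to first self-poisoning and is not described as men only, and none of them is the trial's 25 sites. The illustration supports a range from fewer than about 11 to about 54, and no single figure within it.

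**The case against.** The strongest reply is that this is a slip in one phrase. The parenthesis in section 4.3.3 attaches the same any-reason qualifier to three outcomes in a row, which looks like a drafting carry-over, and four other places agree that suicide is excluded. The intended endpoint can therefore be recovered. That is fair, and it limits the seriousness of the point. It does not remove it, because section 4.3.3 is the operative text for the analysis and whoever implements it would have to choose between that section and the outcome definitions.

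A reader might infer that objective 6 is left with no analysis. The documents do not support that: the sentence covers all binary secondary outcomes and assigns them the primary outcome's method, so the method for non-suicide mortality is fixed. Only the endpoint named is wrong.

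A reader might also take about 54 suicides as the expected number. The Ontario figure in the same section points to a much smaller one, so 54 is the top of a range.

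On the data sources, a reader might conclude that NACRS would miss inpatient admissions and that DAD should replace it. The protocol does not say whether NACRS records admissions, and it does not establish DAD as the complete or correct source. Taking counts from one database and costs from another is not in itself a contradiction. All that stands is an unexplained difference within Table 2.

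**Conclusion.** The mortality point holds as a conflict in the text. Section 4.3.3 would model an endpoint that includes suicides, contrary to the registration data set, objective 6, section 4.1.4 and Table 2, and the result would not answer objective 6. The handling of undetermined deaths is also inconsistent, between the registration data set and the other three definitions. These conclusions rest on the wording alone and need no outside assumption.

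The size is uncertain: from fewer than about 11 to about 54 suicides among 2,000 men followed for a year, if one or other of the cited rates applied to these sites. The primary outcome and the power calculation are not touched. The point should be corrected, and it is confined to one secondary outcome.

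The NACRS and DAD difference is a minor query held with low confidence. It is not shown that any admission would be missed.

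**What to change.** 1. In section 4.3.3, replace the all-cause mortality item in the list of binary secondary outcomes with mortality from causes other than suicide.
2. Choose one rule for undetermined deaths and state it identically in the registration data set, section 3.3.2, section 4.1.4, Table 2 and section 4.3.3.
3. Ask the sponsor to confirm that NACRS is the intended source for hospital admissions and previous hospitalizations, or to reconcile those rows of Table 2 with the source used for hospitalization costs.

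The first two are wording edits. They need no new data, since Table 2 already names the death database for both suicide and other mortality, and they leave the design and sample size unchanged. The third is a query to the sponsor. The mortality wording should be settled before outcome data are analysed, so that the choice of definition cannot be influenced by the results.
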